The following AEs will require the collection of information sufficient to provide a detailed description of the event, treatment and outcome to the Medical Monitor for the study: any treatment-emergent significant laboratory abnormality; any seizures, herpes zoster infection, severe infection; any moderate to severe drug rash or any rash lasting more than 72 hours (regardless of severity); amyloid-related imaging abnormalities (vasogenic edema, macrohemorrhage, an area of superficial siderosis, or a new microhemorrhage); a “yes” answer to Type 4 or 5 suicidal ideation, or a “yes” response to any suicidal behavior on the C-SSRS.

All AEs must be followed through the final Follow-Up visit (Visit 20), or until resolution, whichever comes first. All SAEs must be followed to resolution or, if resolution is unlikely, to stabilization. (revised per Amendment 04)

Every effort must be made by the investigator to categorize each AE according to its severity and its relationship to the study treatment.

Assessing Severity of Adverse Events

AEs will be graded on a 3-point scale (mild, moderate, severe) and reported in the detail indicated on the eCRF. The definitions are as follows:

- | | |
|----------|--|
| Mild | Discomfort noticed, but no disruption of normal daily activity |
| Moderate | Discomfort sufficient to reduce or affect normal daily activity |
| Severe | Incapacitating, with inability to work or to perform normal daily activity |

The criteria for assessing severity are different than those used for seriousness (see [Section 9.5.1.5.2](#) for the definition of an SAE).

Assessing Relationship to Study Treatment

Items to be considered when assessing the relationship of an AE to the study treatment are:

- Temporal relationship of the onset of the event to the initiation of the study treatment
- The course of the event, especially the effect of discontinuation of study treatment or reintroduction of study treatment, as applicable
- Whether the event is known to be associated with the study treatment or with other similar treatments
- The presence of risk factors in the study subject known to increase the occurrence of the event
- The presence of nonstudy, treatment-related factors that are known to be associated with the occurrence of the event

Classification of Causality

The relationship of each AE to the study drug will be recorded on the eCRF in response to the following question:

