9.5.1.5.2 SERIOUS ADVERSE EVENTS AND EVENTS ASSOCIATED WITH SPECIAL SITUATIONS

An SAE is any untoward medical occurrence that at any dose:

- Results in death
- Is life-threatening (ie, the subject was at immediate risk of death from the AE as it occurred; this does not include an event that, had it occurred in a more severe form or was allowed to continue, might have caused death)
- Requires inpatient hospitalization or prolongation of existing hospitalization
- Results in persistent or significant disability/incapacity
- Is a congenital anomaly/birth defect (in the child of a subject who was exposed to the study drug)

Other important medical events that may not be immediately life-threatening or result in death or hospitalization but, when based on appropriate medical judgment, may jeopardize the subject or may require intervention to prevent one of the outcomes in the definition of SAE listed above should also be considered SAEs. Medical and scientific judgment should be exercised in deciding whether expedited reporting is appropriate in such situations.

For this study, the following events should always be considered serious and reportable using the criteria of important medical event if the event does not meet other serious criteria: new onset seizures, ocular herpes.

In addition to the above, events associated with special situations include pregnancy or exposure to study drug through breastfeeding; AEs associated with study drug overdose, misuse, abuse, or medication error. These events associated with special situations are to be captured using the SAE procedures but are to be considered as SAEs only if they meet one of the above criteria. All AEs associated with special situations are to be reported on the eCRF whether or not they meet the criteria for SAEs.

All SAEs must be followed to resolution or, if resolution is unlikely, to stabilization.

The following hospitalizations are not considered to be SAEs because there is no “AE” (ie, there is no untoward medical occurrence) associated with the hospitalization:

- Hospitalizations for respite care
- Planned hospitalizations required by the protocol
- Hospitalization planned before informed consent (where the condition requiring the hospitalization has not changed after study drug administration)
- Hospitalization for administration of study drug or insertion of access for administration of study drug

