9.5.4.1 Reporting of Serious Adverse Events

All SAEs, regardless of their relationship to study treatment, must be reported on a completed SAE form by email or fax as soon as possible but no later than 24 hours from when the investigator becomes aware of the event.

SAEs, regardless of causality assessment, must be collected up to 3 months after the last dose of study drug, ie, through to the final follow-up visit (Visit 20). (revised per Amendment 04) (revised per Amendments 04 and 05) However, any SAEs volunteered by subjects after this time point must be reported according to standard procedures. All SAEs must be followed to resolution or, if resolution is unlikely, to stabilization. Any SAE judged by the investigator to be related to the study treatment or any protocol-required procedure should be reported to the sponsor regardless of the length of time that has passed since study completion.

The detailed contact information for reporting of SAEs is provided in the Investigator Study File.

For urgent safety issues, please ensure all appropriate medical care is administered to the subject and contact the appropriate study team member listed in the Investigator Study File.

It is very important that the SAE report form be filled out as completely as possible at the time of the initial report. This includes the investigator's assessment of causality.

Any follow-up information received on SAEs should be forwarded within 1 business day of its receipt. If the follow-up information changes the investigator's assessment of causality, this should also be noted on the follow-up SAE form.

Preliminary SAE reports should be followed as soon as possible by detailed descriptions including copies of hospital case reports, autopsy reports, and other documents requested by the sponsor.

The investigator must notify his/her IRB/IEC of the occurrence of the SAE in writing, if required by their institution. A copy of this communication must be forwarded to the sponsor, or its designee, to be filed in the sponsor's Trial Master File.

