- c. Subjects with clinical evidence of infection will have their CD4 (T helper cells), CD8 (cytotoxic T cells), and CD19 (B cells) absolute counts measured. Blood and other biological samples will also be collected for investigations of infective pathogens (eg, serological tests, quantitative polymerase chain reaction, microscopy, and culture) where appropriate. In subjects with infection, if any of their absolute cell counts meets the discontinuation thresholds, study drug will be discontinued. All subjects with severe infections will be discontinued from study drug. All subjects with herpes zoster

(shingles) or ocular herpes infections will be discontinued from study drug, regardless of severity of presentation. Subjects with mild or moderate infection may continue treatment with study drug unless otherwise clinically indicated or otherwise specified below. Specifically, when any of the CD4 (T helper cells), CD8 (cytotoxic T cells), and CD19 (B cells) absolute counts are between the population-adjusted LLN and the discontinuation thresholds, subjects with infections of moderate intensity will be discontinued from study drug (eg, subjects whose infections are not localized, or subjects who are systemically unwell, or who require systemic anti-infective drug treatment). All subjects with infection who are discontinued from study drug will be followed for a period of 12 weeks or until the infection resolves/ stabilizes or until the CD4 (T helper cells), CD8 (cytotoxic T cells), and CD19 (B cells) absolute counts have returned to greater than population-adjusted LLN (whichever comes latest). (revised per Amendments 02 and 04)

Table 2 Study Drug Actions for Lymphocyte Subset Absolute Counts and Infection

| Criterion | Severity of Infection | | | |
|--|--|---|---|------------------------|
| | None | Mild | Moderate | Severe |
| CD4 (T helper cells), CD8 (cytotoxic T cells), or CD19 (B cells) absolute counts below discontinuation threshold | If confirmed with repeat testing within 1 week, then temporarily suspend study drug as per instructions above. | Discontinue study drug | Discontinue study drug | Discontinue study drug |

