| CD4 (T helper cells), CD8 (cytotoxic T cells), or CD19 (B cells) absolute counts between population-adjusted LLN and discontinuation threshold | May continue treatment with study drug unless discontinuation is clinically indicated | May continue treatment with study drug unless discontinuation is clinically indicated | Discontinue study drug | Discontinue study drug |
| CD4 (T helper cells), CD8 (cytotoxic T cells), or CD19 (B cells) absolute counts always > population-adjusted LLN | May continue treatment with study drug unless discontinuation is clinically indicated | May continue treatment with study drug unless discontinuation is clinically indicated | May continue treatment with study drug unless discontinuation is clinically indicated (See (e) for exception) | Discontinue study drug |

LLN = lower limit of normal.

(Table revised per Amendments 02 and 04)

- d. A subject with any skin rash of moderate to severe intensity, or any rash lasting more than 72 hours regardless of severity (see (e) for exception), will be discontinued from study drug and a dermatological consult will be requested regardless of whether the rash is considered drug-related or due to other causes. For cases where the investigator suspects a drug rash, regardless of severity, the subject will be discontinued from study

drug, a dermatological consult will be requested, and a skin biopsy will be performed to confirm the diagnosis. The skin rash will be treated as per standard care and will be followed up until resolution regardless of etiology or severity.

- e. Subjects who develop moderate to severe oral or genital herpes should be discontinued from study drug. Subjects who develop a mild case of oral or genital herpes may remain on study drug even if the event lasts more than 72 hours.

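### Table 2 of Section 9.3.3 leaves to clinical judgment a stop that rule (c) makes mandatory for herpes zoster and ocular herpes

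*Protocol*

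**What the plan says.** Section 9.3.3 lists the safety criteria for stopping study drug as items (a) to (j). Item (c) deals with infection. Its rule for herpes zoster and ocular herpes has no threshold of severity or cell count: "shingles) or ocular herpes infections will be discontinued from study drug, regardless of severity of presentation". The next sentence of (c) lets mild or moderate infection continue in general, subject to clinical indication and to anything specified further down. Item (c) then requires a stop for moderate infection when any of CD4, CD8 or CD19 lies between the population-adjusted lower limit of normal (LLN) and the discontinuation threshold. Its examples of moderate infection are "subjects whose infections are not localized, or subjects who are systemically unwell, or who require systemic anti-infective drug treatment".

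Table 2 follows and sets the action by three count rows and by infection severity. The cell for moderate infection with counts always above the LLN reads "May continue treatment with study drug unless discontinuation is clinically indicated (See (e) for exception". Two mild cells (counts between the LLN and the threshold, and counts above the LLN) have the same permissive wording with no exception. The notes under the table give only an abbreviation and the revision history.

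Item (e), the one the table points to, says: "Subjects who develop moderate to severe oral or genital herpes should be discontinued from study drug". It does not mention zoster or ocular herpes. Item (d) stops drug for moderate to severe rash and for "any rash lasting more than 72 hours regardless of severity".

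**The concern.** Rule and table give different answers for the same subject. Under (c), a subject with mild ocular herpes must stop. Under Table 2, with counts above the discontinuation threshold, the same subject may stay on drug unless the investigator thinks otherwise.

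Two features make the omission easier to act on. First, the table does flag a herpes exception, but only the one in (e). A reader could take that as the complete set, although the stricter rule is the one left out. Second, the general sentence in (c) that lets mild or moderate infection continue yields only to what is specified below it, while the zoster and ocular stop stands above it.

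What is at stake is conduct and subject safety. Immune effects are the drug's main safety concern in this protocol, and Section 9.2.5 gives the step from 14 days to 18 months of dosing as a reason for rules of this kind. No endpoint or analysis is involved.

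**Working it through.** No formula applies. The check compares Table 2 cell by cell with rules (c), (d) and (e). The column for no infection is left out, because the zoster and ocular rule cannot apply there.

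**Step 1. Count the cells.** 3 count rows × 3 severities (mild, moderate, severe) = 9 infection cells.

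| Counts | Mild | Moderate | Severe |
|---|---|---|---|
| Below discontinuation threshold | Stop | Stop | Stop |
| Between LLN and threshold | Judgment | Stop | Stop |
| Always above LLN | Judgment | Judgment, exception to (e) | Stop |

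Stop: 3 + 2 + 1 = 6. Judgment: 0 + 1 + 2 = 3. Judgment cells with any exception: 1. Judgment cells reflecting the zoster and ocular stop: 0.

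**Step 2. Remove what other rules already catch.**

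- *Moderate-infection rule in (c).* Need for systemic anti-infective treatment is one of its examples of moderate infection, and moderate infection with counts between the LLN and the threshold is already a stop. The mild cell in that row is therefore affected only for cases that do not need such treatment, that is, in part.
- *Rash rule (d).* Zoster rash of moderate or severe intensity, and any rash beyond 72 hours, is already a stop. For zoster that leaves a mild rash within its first 72 hours. Ocular herpes without skin rash is untouched by (d).

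**Step 3. What remains at judgment.**

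| Infection | In full | In part |
|---|---|---|
| Ocular herpes without skin rash | 2 cells: mild and moderate, counts above LLN | 1 cell: mild, counts between |
| Zoster, mild rash up to 72 hours | 1 cell: mild, counts above LLN | 1 cell: mild, counts between |

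The zoster line is cautious. If the systemic-treatment example were also used to classify infections when counts are above the LLN, an early mild zoster rash needing systemic treatment would move to the moderate cell of that row. That cell also leaves the decision to judgment.

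**Step 4. After the fix.** With a footnote on the three cells pointing to (c), 0 of 9 infection cells would leave zoster or ocular herpes to judgment.

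**The case against.** The strongest reply is that nothing in the table is false. No cell requires the subject to continue, the permissive wording leaves room for a mandatory stop, and (c) stands immediately above the table. Table 2 covers counts and severity and does not claim to be the whole of Section 9.3.3. It also omits the MRI, QTcF, seizure and pregnancy criteria, and Sections 9.1.2.1 and 9.4.1 send sites to Section 9.3.3 as a whole. The pointer to (e) may exist only because (e) comes after the table, whereas (c) comes just before it.

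There are also safeguards:

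- Section 9.5.1.5.2 makes ocular herpes always reportable as serious "if the event does not meet other serious criteria: new onset seizures, ocular herpes", and Section 9.5.4.1 requires the report "no later than 24 hours from when the investigator becomes aware of the event".
- Section 9.5.1.5.1 asks for a detailed description to the Medical Monitor of "any seizures, herpes zoster infection, severe infection".
- Section 9.4.1 prompts discussion of suspending dosing during a concurrent illness.
- Section 9.5.1.5.8 has subjects asked about new skin and conjunctival lesions at each visit.
- Section 9.2.5 names shingles among the discontinuation criteria.
- Section 9.3.2 excludes a history of ophthalmic shingles or ocular herpes simplex.

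Finally, the Amendment 06 text of Section 9.3.3 is not shown, so the gap may already be closed.

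Most of this stands and limits the point to a minor one. It does not remove it. MRI, QTcF, seizure and pregnancy lie outside the table's subject, but zoster and ocular herpes are infections, and infection is what the table sets actions for. The safeguards would probably bring a missed stop to the sponsor's attention, but none puts the stop in the table. The suspension in Section 9.4.1 is also a different action: dosing may resume after it, whereas Section 9.5.5 bars a restart after early discontinuation.

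**Conclusion.** The point holds and is minor. In the Amendment 05 text, three of nine infection cells in Table 2 leave to judgment what (c) makes mandatory for herpes zoster and ocular herpes, and the table's only exception points to a different set of herpes infections. The exposure is limited to a site that works from the table without (c), and then mainly to the residual cases in the working. How often that would happen cannot be estimated from the protocol, and no effect on the sample size or analyses is claimed. The conclusion rests on reading Table 2 as an action table that sites may use directly. It applies only to the version shown.

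**What to change.** Leave (c) as it is. First confirm that the Amendment 06 version of Table 2 still has the gap. If it does, attach one footnote to the three cells (mild with counts between the LLN and the threshold, mild with counts above the LLN, moderate with counts above the LLN): *Herpes zoster and ocular herpes: discontinue study drug regardless of severity or lymphocyte counts, see (c).*

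The cost is one table footnote and a notice to sites. Assessments, sample size and analyses do not change.

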9.4 Treatments

9.4.1 Treatments Administered

For this study the test drug is E2609 and the control drug is placebo. All study drugs are to be administered orally, QD, with food.

Treatments to be administered are 5, 15, and 50 mg E2609 or placebo as shown below and in [Figure 1](#). (revised per Amendments 01 and 05) Study treatment will begin on Day 1 (at the study site) following Randomization and will continue for approximately 78 weeks. Please refer to [Table 7](#) and [Section 9.5.1.4.1](#) for specific information on drug administration on days when PK sampling is to be performed.

Study drug doses will remain the same for each individual subject unless the interim PK/PD analysis determines that an entire dose level requires adjustment (Section 9.4.4). See Section 9.3.3 for safety-related discontinuation criteria of study drug. If a subject develops a concurrent illness during the treatment period, the investigator should discuss with the medical monitor on whether dosing with study drug needs to be temporarily suspended. As a general clinical guideline, dosing with study drug may be resumed after resolution or stabilization of the concurrent illness, after discussion with the medical monitor.

9.4.2 Identity of Investigational Product

E2609 tablets of 5-, 10-, and 25-mg dose strengths will be supplied. Placebo tablets of identical appearance will also be available. Each subject will receive 2 tablets, which combined will make up the required doses of E2609 5, 15, 50 mg, or placebo. The tablets will be supplied by the Sponsor in labeled blister packs. The product release certificates for E2609 and placebo will be included in the clinical study report for this protocol.

Subjects will be stratified and randomized, and drug will be dispensed, via an interactive voice and web response system (IxRS) system (see Section 9.4.3).

The sponsor will provide the study drugs packaged in a double-blind configuration. Each subject's study tablets will consist of either E2609 or placebo, or both (see Section 9.4.2.3 for labeling details).

9.4.2.1 Chemical Name and Formula of E2609

- Test drug code: E2609
- Generic name: not applicable
- Chemical name: International Union of Pure and Applied Chemistry
- *N*-{3-[(4*aS*,5*R*,7*aS*)-2-Amino-5-methyl-4*a*,5-dihydro-4*H*furo[3,4-*d*][1,3]thiazin-7*a*(7*H*)-yl]-4-fluorophenyl}-5-(difluoromethyl)pyrazine-2-carboxamide
- Molecular formula: C₁₉H₁₈F₃N₅O₂S
- Relative molecular mass: 437.44

9.4.2.2 Comparator Drug

Not applicable.

9.4.2.3 Labeling for Study Drug

E2609 will be labeled in accordance with text that is in full regulatory compliance with each participating country and is translated into the required language(s) for each of those countries. The following information may be included but is not limited to:

- Protocol number
- For clinical study use only

- Name and address of the sponsor
- Chemical name/drug identifier (ID)
- Lot number/batch number
- Storage conditions, expiration date if necessary

9.4.2.4 Storage Conditions

Study drug will be stored in accordance with the labeled storage conditions. Temperature monitoring is required at the storage location to ensure that the study drug is maintained within an established temperature range. The investigator or designee (or if regionally required, the head of the medical institution) is responsible for ensuring that the temperature is monitored throughout the total duration of the study and that records are maintained; the temperature should be monitored continuously by using either an in-house validated data acquisition system, a mechanical recording device, such as a calibrated chart recorder, or by manual means, such that minimum and maximum thermometric values over a specific time period can be recorded and retrieved as required.

9.4.3 Method of Assigning Subjects to Treatment Groups

Subjects will be assigned to treatments based on a computer-generated randomization scheme. The randomization scheme and identification for each subject will be included in the final clinical study report for this study. The doses and number of treatment groups are described in [Section 9.4.1](#). (revised per Amendments 01 and 05)

Randomization will be performed centrally by an IxRS. The IxRS or clinical supply vendor will generate the randomized blister card identification numbers. At enrollment, the investigator or designee will call the IxRS to register the subject information. At randomization (Visit 3), the IxRS will assign each subject a unique randomization number.

9.4.4 Selection of Doses in the Study

It is not known how the level of CSF or brain A β reduction is related to clinical efficacy. Therefore, in this study, doses will be selected such that at steady state, they will result in 25%, 50%, and 75% reduction in CSF A β levels from baseline to cover a broad range of PD effects.

In Study 007, the relative bioavailability of a tablet formulation of E2609 in the fed and the fasted states compared with the capsule formulation in the fasted state (used in Studies 001 and 002) was investigated. It was found that when the tablet form of E2609 (50 mg) was administered with food, the exposure (ie, AUC) of the parent drug E2609 was higher, with lower maximum observed concentrations and reduced exposure to the metabolites, compared with either formulation in the fasted state.

Based on the PK/PD modeling using data from healthy volunteer Studies 001, 002, and 007, doses of 5, 15, and 50 mg QD administered as the tablet formulation with food in this study should achieve CSF A β reduction from baseline of approximately 25%, 50%, and 75% at steady state, respectively ([Table 3](#)).

Table 3 Predicted Steady State Plasma PK Parameters and CSF Amyloid β Reduction From Baseline

| E2609 Tablet Daily Dose (mg) With Food | E2609 Plasma $C_{max,ss}$ (ng/ml) | E2609 Plasma $C_{ss,av}$ (ng/ml) | E2609 Plasma $AUC_{(0-24h)ss}$ (ng.h/ml) | % Reduction CSF BACE1 Activity | % Reduction CSF $A\beta(1-x)$ |
|---|---|--|--|---------------------------------------|---|
| 5 | 6.2 | 3.3 | 80.3 | 16.2 | 33 |
| 15 | 18.6 | 10 | 240.9 | 36.6 | 56 |
| 50 | 62.1 | 33.5 | 803.0 | 65.7 | 79 |

$A\beta(1-x)$ = amyloid beta monomer from amino acid 1 to x, $AUC_{(0-24h)ss}$ = area under the concentration x time curve at steady state from time zero to 24 hours, BACE1 = beta-amyloid converting enzyme, CSF = cerebrospinal fluid, $C_{ss,av}$ = average steady-state concentration, $C_{max,ss}$ = maximum plasma concentration at steady state, PK = pharmacokinetics.

The PK/PD modeling described above, which was conducted using data obtained from healthy volunteers, has also been supported by modeling of data from subjects with an underlying AD pathology (Study 101). Furthermore, external data with another BACE1 inhibitor (MK-8931) showed a similar PD effect in AD patients as in healthy volunteers (Forman, et al., 2013). Therefore we are confident that the modeling of E2609 effects in healthy subjects will be applicable for both MCI/Prodromal and mild to moderate AD dementia patients. (revised per Amendment 01)

The exposure of the highest dose in this study (50 mg QD tablet administered with food) is less than that of the 100 mg QD dose (capsule administered fasted) in Study 002.

The 100 mg QD dose administered for 14 days in Study 002 was well tolerated with no clinically significant changes in laboratory parameters, vital signs, or ECG parameters. On Day 15, for the 100 mg QD cohort in Study 002, there was a reduction of CD4 lymphocyte counts compared with placebo (CD4 lymphocyte counts on E2609 decreased by 3.1% from baseline, whereas the placebo control showed an increase of 8.7%), but this decrease was less than that observed at doses of 200 mg (22.9% decrease) or 400 mg (17.3% decrease). No subject had infections or drug rash while receiving E2609 100 mg QD or at lower doses in Study 002, whereas at 200 and 400 mg QD, 4 subjects had symptomatic orolabial HSV1 relapses and 2 subjects at the highest dose had drug rash. The highest dose for Study 202 of 50 mg QD (tablet administered with food) is therefore expected to have a similar or better safety profile compared with the 100 mg QD capsule (administered fasted) in Study 002. Specific exclusion criteria, blinded and unblinded safety monitoring procedures, and safety criteria for discontinuation from study drug are included in this study in order to mitigate any immunology-related risk with E2609, particularly in light of the progression from 14 days of dosing (Study 002) to 18 months of dosing in this study.

Interim analyses of the E2609 plasma PK for all subjects and the E2609CSF PK and PD profiles will be performed on baseline data and samples collected after at least 4 weeks of treatment. These interim analyses, as well as analyses of safety data, will be performed on an ongoing basis. Refer Section 9.7.3 for more detail. The median and mean percentage change from baseline in CSF $A\beta(1-x)$ measured after 4 weeks of treatment for each dose of E2609 and its 90% confidence interval for the median will be derived. In addition, exploratory PK/PD modeling will be conducted. This PK/PD modeling will use the observed PK and PD

data and will relate the average steady state plasma concentration of E2609 to steady state CSF A β (1-x) percentage reduction from baseline after at least 4 weeks of dosing. (revised per Amendments 01, 02, 03, 04, and 05)

